2. INTRODUCTION

Nirmatrelvir, a potent and selective SARS-CoV-2 3CL orally administered protease inhibitor, is being investigated in participants with rebound of COVID-19 symptoms and rapid antigen test positivity.

The purpose of this study is to evaluate the efficacy, safety and tolerability of a second 5-day treatment course of nirmatrelvir/ritonavir in participants with a rebound in COVID-19 symptoms and a positive rapid antigen test within 2 weeks (14 days) following completion of an initial 5-day treatment course.

This statistical analysis plan (SAP) provides the detailed methodology for summary and statistical analyses of the data collected in Study C4671042.

2.1. Modifications to the Analysis Plan Described in the Protocol

Not Applicable.

2.2. Study Objectives, Endpoints, and Estimands

Objectives	Endpoints	Estimands
Primary:	Primary:	Primary:

 To compare the effect of nirmatrelvir/ritonavir to placebo/ritonavir on viral RNA level in NP swabs in participants with mild-to-moderate COVID-19. 	
 The change in viral SARS-CoV-2 RNA level as measured in NP swabs from baseline to Day 5. 	
 The difference in mean change of SARS-CoV-2 RNA level in NP swabs from baseline to Day 5 between nirmatrelvir/ritonavir and placebo/ritonavir group in participants with a rebound in COVID-19 symptoms and a positive rapid antigen test within 2 weeks following completion of an initial 5-day treatment course ,who have a positive viral RNA NP swab test result at baseline. This will be estimated without regard to study treatment discontinuation and without regard to prohibited therapies.

Objectives	Endpoints	Estimands
Secondary:	Secondary:	Secondary:

 To compare the effect of nirmatrelvir/ritonavir to placebo/ritonavir on the duration of viral shedding. 	
 Time to 2 consecutive negative rapid antigen test results obtained at least 24 (-2) h apart through Day 28. 	
 The hazard ratio for time to 2 consecutive negative rapid antigen test results obtained at least 24 (-2) h apart through Day 28 between nirmatrelvir/ritonavir and placebo/ritonavir group in participants with rebound in COVID-19 symptoms and a positive rapid antigen test within 2 weeks following completion of an initial 5-day treatment course, who have a positive viral RNA NP swab test result at baseline. This will be estimated without regard to study treatment discontinuation and without regard to prohibited therapies.

 To compare the effect of nirmatrelvir/ritonavir to placebo/ritonavir on the duration and severity of signs and symptoms in participants with mild-to-moderate COVID-19. 	
 Time (days) to sustained alleviation of all targeted signs and symptoms through Day 28 where sustained alleviation is defined as the first of 2 consecutive days when any symptoms scored as moderate or severe at baseline are scored as mild or absent and any symptoms scored as mild or absent at baseline are scored as absent. 	
 The hazard ratio for time to sustained alleviation of all targeted signs and symptoms through Day 28 between nirmatrelvir/ritonavir and placebo/ritonavir group in participants with rebound in COVID-19 symptoms and a positive rapid antigen test within 2 weeks following completion of an initial 5-day treatment course, who have a positive viral RNA NP swab test result at baseline. This will be estimated without regard to study treatment discontinuation and without regard to prohibited therapies.

 To describe the safety and tolerability of nirmatrelvir/ritonavir in participants with mild-to-moderate COVID-19. 	
 Incidence of TEAEs. Incidence of SAEs and AEs leading to discontinuation. 	
 Not applicable.
Tertiary/Exploratory:	Tertiary/Exploratory:	Tertiary/Exploratory:

 To compare the effect of nirmatrelvir/ritonavir to placebo/ritonavir on viral RNA level in NP swabs in participants with mild-to-moderate COVID-19. 	
 Proportion of participants with SARS-CoV-2 RNA in NP swab below the LLOQ on Days 3, 5, 10, 15, 21, 28, and 34. Proportion of participants with sustained NP swab SARS-CoV-2 RNA below the LLOQ (defined as $<2.0 \log_{10}$ copies/mL) from Day 5 through Day 34. Proportion of participants with SARS-CoV-2 RNA in NP swabs below the LLOQ (defined as 	
 Not applicable.

Objectives	Endpoints	Estimands
	
<2.0 \log_{10} copies/mL) on both Days 5 and 10.
 
 The change in SARS-CoV-2 RNA level in NP swabs from baseline to Days 3, 10, 15, 21, 28, and 34. Time to sustained NP swab SARS-CoV-2 RNA below the LLOQ (defined as <2.0 \log_{10} copies/mL) and remains below the LLOQ through Day 34 for participants with NP swab SARS-CoV-2 RNA greater than or equal to the LLOQ at baseline. Rebound in SARS-CoV-2 RNA level in NP swabs at follow-up (ie, any study visit from Day 10 to through Day 34, defined as a half (0.5) \log_{10} copies/mL increase or greater in SARS-CoV-2 RNA level relative to SARS-CoV-2 RNA level on Day 5 and with a follow-up viral RNA level $\geq 2.5 \log_{10}$ copies/mL. 	

 To compare the effect of nirmatrelvir/ritonavir on the rate of cell culture infectious virus over time in participants with mild-to-moderate COVID-19 	
In participants with detectable viral titers at baseline by TCID50:
 
 Time to negative infectious titer by TCID50. Change in TCID50 from baseline to Days 3, 5, 10, 15, 21, 28, and 34. Proportion of participants with negative infectious titer by TCID50 on Days 3, 5, 10, 15, 21, 28, and 34. 
In participants with positive viral titers at baseline by virus recovery:
 
 Time to negative infectious titer by virus recovery. Proportion of participants with negative infectious titer by virus recovery on Days 3, 5, 10, 15, 21, 28, and 34. 	
 Not applicable

 To compare the effect of nirmatrelvir/ritonavir to placebo/ritonavir on viral concentration in plasma in participants with mild-to-moderate COVID-19. 	
 Change from baseline in SARS-CoV-2 viral RNA level in plasma, over time. 	
 Not applicable.

Objectives	Endpoints	Estimands

 To compare the effect of nirmatrelvir/ritonavir to placebo/ritonavir on COVID-19-related hospitalization and all-cause mortality in participants with mild-to-moderate COVID-19. 	
 Proportion of participants with COVID-19-related hospitalization >24h or death from any cause through Day 28. 	
 Not applicable.

 To compare the effect of nirmatrelvir/ritonavir to placebo/ritonavir on COVID-19-related healthcare resource utilization in participants with mild-to-moderate COVID-19. 	
 Number of COVID-19-related medical visits through Day 34. 	
 Not applicable.

 To compare the effect of nirmatrelvir/ritonavir to placebo/ritonavir on the duration and severity of signs and symptoms in participants with mild-to-moderate COVID-19. 	
 Time (days) to sustained resolution of all targeted signs and symptoms through Day 28 where sustained resolution is defined as the first of two consecutive days when all targeted COVID-19 symptoms are scored as absent. 	
 Not applicable

2.2.1. Primary Estimand(s)

The primary estimand is the difference in mean change of SARS-CoV-2 RNA level in NP swabs from baseline to Day 5 between nirmatrelvir/ritonavir and placebo/ritonavir group in patients with a rebound in COVID-19 symptoms and a positive rapid antigen test within 2 weeks following completion of an initial 5-day treatment course, who have a positive viral RNA NP swab test result at baseline. This will be estimated without regard to study treatment discontinuation and without regard to prohibited therapies.

2.2.2. Secondary Estimand(s)

Estimands for the secondary endpoints are:

- The hazard ratio for time to 2 consecutive negative rapid antigen test results obtained at least 24 (-2) h apart through Day 28 between nirmatrelvir/ritonavir and placebo/ritonavir group in participants with rebound in COVID-19 symptoms and a positive rapid antigen test within 2 weeks following completion of an initial 5-day treatment course, who have a positive viral RNA NP swabtest result at baseline. This will be estimated without regard to study treatment discontinuation and without regard to prohibited therapies.
- The hazard ratio for time to sustained alleviation of all targeted signs and symptoms through Day 28 between nirmatrelvir/ritonavir and placebo/ritonavir group in participants with rebound in COVID-19 symptoms and a positive rapid antigen test within 2 weeks following completion of an initial 5-day treatment course, who have a positive viral RNA NP swabtest result at baseline. This will be estimated without regard to study treatment discontinuation and without regard to prohibited therapies.

2.3. Study Design

This Phase 2, randomized, double-blind, placebo-controlled study will evaluate the efficacy and safety of a repeat 5-day treatment course of nirmatrelvir/ritonavir or placebo/ritonavir for the treatment of mild-to-moderate COVID-19. Participants must have written documentation, such as an electronic health record, medical record, or prescription receipt of treatment with nirmatrelvir/ritonavir (verbal assertion of treatment is not acceptable) with patient-reported 100% compliance (ie, completed a 5 day course of nirmatrelvir/ritonavir). They must have experienced alleviation or resolution in COVID-19 signs/symptoms followed by a worsening (rebound) of signs/symptoms along with a positive rapid antigen test after completing an initial 5-day course of nirmatrelvir/ritonavir.

The onset of rebound in COVID-19 symptoms along with evidence of SARS-CoV-2 infection must occur within 2 weeks (14 days) after completion of an initial 5-day course of nirmatrelvir/ritonavir. A 2-week time-period for rebound symptoms and SARS-CoV-2 infection was selected to enroll a population that has a presumptive recurrence of the same viral illness and not a new SARS-CoV-2 infection. Symptom burden including alleviation, resolution and worsening (rebound) to qualify for the study is based on the judgment of both the participant along with investigator judgment.

Eligible participants for this study will be randomly assigned (2:1 allocation of active to placebo) to receive:

- nirmatrelvir plus ritonavir orally q12h for 5 days; or
- placebo plus ritonavir orally q12h for 5 days.

Randomization will be stratified by geographic region.

Participants will be screened within 24 hours before randomization.

[figure not shown]
Participants must be randomized within 48 hours from the onset of the rebound COVID-19 symptoms and must be randomized within 24 hours of a positive baseline rapid antigen test. The total study duration is up to 24 weeks, including study intervention administration through Day 5 or Day 6, efficacy and safety assessments through Day 34, and long-term follow up at Weeks 12 and 24.

Participants are eligible if they are at least 12 years of age (and weigh ≥ 40 kg at screening) and they must have at least 1 characteristic or underlying medical condition associated with an increased risk of developing severe illness from COVID-19. However, participants who are immunocompromised are excluded from this study as they may have prolonged viral shedding due to their immunocompromised state. Participants will be eligible for enrollment irrespective of COVID-19 vaccination/boosted status (except for time course restrictions listed in the exclusion criteria).

An independent E-DMC will review unblinded data to ensure the safety of participants on an ongoing basis throughout the duration of the study.

The study schematic is provided in Figure 1.

Figure 1. Study Schema

2.4. Sample Size Determination

The study will enroll approximately 411 participants.

The sample size calculation is based on the primary efficacy endpoint as the change in viral RNA level from baseline to Day 5 as measured in NP swabs in the MITT analysis set. Assuming a SD of 1.8 (based on EPIC-HR, NCT04960202), a sample size of approximately 315 evaluable participants (210 participants in nirmatrelvir/ritonavir group and 105 participants in placebo/ritonavir group) is expected to provide 90% power to detect a difference of 0.7 \log_{10} copies/mL in viral RNA between groups using a 2-sided 0.05 alpha level test. Assuming approximately 10% of participants will have a negative viral RNA result at baseline, and assuming a non-evaluable rate of 15%, approximately 411 participants will be randomized in the study to achieve approximately 315 participants evaluable for the primary efficacy endpoint.

3. ENDPOINTS AND BASELINE VARIABLES: DEFINITIONS AND CONVENTIONS

3.1. Primary Endpoint(s)

- The primary endpoint is the change in viral SARS-CoV-2 RNA level as measured in NP swabs from baseline to Day 5.

3.2. Secondary Endpoint(s)

- Time to 2 consecutive negative rapid antigen test results obtained at least 24 (-2) h apart through Day 28.

- Time (days) to sustained alleviation of all targeted signs and symptoms through Day 28 where sustained alleviation is defined as the first of 2 consecutive days when any symptoms scored as moderate or severe at baseline are scored as mild or absent and any symptoms scored as mild or absent at baseline are scored as absent.
- Incidence of TEAEs. Incidence of SAEs and AEs leading to discontinuation.

3.3. Tertiary/Exploratory Endpoint(s)

- Proportion of participants with SARS-CoV-2 RNA in NP swab below the LLOQ on Days 3, 5, 10, 15, 21, 28, and 34.
- Proportion of participants with sustained NP swab SARS-CoV-2 RNA below the LLOQ (defined as $<2.0 \log_{10}$ copies/mL) from Day 5 through Day 34.
- Proportion of participants with SARS-CoV-2 RNA in NP swabs below the LLOQ (defined as $<2.0 \log_{10}$ copies/mL) on both Days 5 and 10.
- The change in SARS-CoV-2 RNA level in NP swabs from baseline to Days 3, 10, 15, 21, 28, and 34.
- Time to sustained NP swab SARS-CoV-2 RNA below the LLOQ (defined as $<2.0 \log_{10}$ copies/mL) and remains below the LLOQ through Day 34 for participants with NP swab SARS-CoV-2 RNA greater than or equal to the LLOQ at baseline.
- Rebound in SARS-CoV-2 RNA level in NP swabs at follow-up (ie, any study visit from Day 10 to through Day 34, defined as a half (0.5) \log_{10} copies/mL increase or greater in SARS-CoV-2 RNA level relative to SARS-CoV-2 RNA level on Day 5 and with a follow-up viral RNA level $\geq 2.5 \log_{10}$ copies/mL.
- Time to negative infectious titer by TCID50 in participants with detectable viral titers at baseline by TCID50.
- Change in TCID50 from baseline to Days 3, 5, 10, 15, 21, 28, and 34 in participants with detectable viral titers at baseline by TCID50.
- Proportion of participants with negative infectious titer by TCID50 on Days 3, 5, 10, 15, 21, 28, and 34 in participants with detectable viral titers at baseline by TCID50.
- Time to negative infectious titer by virus recovery in participants with positive viral titers at baseline by virus recovery.
- Proportion of participants with negative infectious titer by virus recovery on Days 3, 5, 10, 15, 21, 28, and 34 in participants with positive viral titers at baseline by virus recovery.

- Change from baseline in SARS-CoV-2 viral RNA level in plasma, over time.
- Proportion of participants with COVID-19-related hospitalization >24h or death from any cause through Day 28.
- Number of COVID-19-related medical visits through Day 34.
- Time (days) to sustained resolution of all targeted signs and symptoms through Day 28 where sustained resolution is defined as the first of two consecutive days when all targeted COVID-19 symptoms are scored as absent.

3.4. Baseline Variables

Baseline visit (Day 1) will be defined as the latest measurement between Day -1 and Day 1.

For viral load data from NP swabs, viral load data from plasma samples, the baseline window will be Day -1 to Day 1, but post-dose samples that are collected within 1 hour post start of dosing will be treated as baseline.

For vital signs, signs and symptoms, and laboratory assessments, the baseline window will be Day -1 to Day 1, without any consideration to the time factor.

3.5. Safety Endpoints

The safety endpoints of this study are:

- Incidence of TEAEs.
- Incidence of SAEs and AEs leading to discontinuations.

Clinical Data Interchange Standards Consortium (CDISC) and Pfizer Standards (CaPS) will be used for the analysis of standard safety data.

3.5.1. Adverse Events

An adverse event (AE) is any untoward medical occurrence in a study participant administered a product or medical device; the event need not necessarily have a causal relationship with the treatment or usage. An AE is considered a treatment-emergent adverse event (TEAE) if the event started on or after the study medication start date and time.

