Previous studies have demonstrated efficacy, safety, and tolerability of nirmatrelvir/ritonavir in adults at increased risk of progressing to severe COVID-19 illness. The FDA has granted EUA for nirmatrelvir/ritonavir for the treatment of mild-to-moderate COVID-19 in adults and pediatric patients (12 years of age and older and weighing at least 40 kg) with positive results of direct SARS-CoV-2 testing, and who are at high risk for progression to severe COVID-19, including hospitalization or death. The most common adverse events described with nirmatrelvir/ritonavir treatment are allergic reactions, change in taste, diarrhea, headache, and vomiting. At present, there are no controlled efficacy and safety data of a repeat 5-day course of nirmatrelvir/ritonavir in participants with acute rebound in symptoms and SARS-CoV-2 infection. People who have rebound in mild-to-moderate COVID-19 may benefit from a repeat 5-day treatment course of nirmatrelvir/ritonavir. Considering the measures to minimize risk to study participants, the potential risks identified in association with nirmatrelvir/ritonavir are justified by the anticipated benefits that may be afforded to participants eligible for enrollment in this study.

Participants will be expected to commit time and may experience some discomfort while undergoing study assessments. In addition, participants must avoid use of a non-study COVID-19 antiviral (excluding a single 5-day treatment course of nirmatrelvir/ritonavir for eligibility), monoclonal antibody therapy for COVID-19, or COVID-19 vaccination within 14 days prior to randomization and through completion of Day 34. Participants who progress to severe or critical COVID-19 will however be permitted to receive specific COVID-19 treatment(s) such as antiviral therapy or use of other treatments considered standard of care. Female participants who are not pregnant and are of childbearing potential must agree to use appropriate contraception methods.

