5.1. Inclusion Criteria

Participants are eligible to be included in the study only if all of the following criteria apply:

Age and Sex:

1. Participants aged 12 years or older and weighing ≥ 40 kg at screening ([Section 10.10.1](#)).
 - Refer to [Appendix 4](#) for reproductive criteria for female ([Section 10.4.1](#)) participants.

Disease Characteristics:

2. Participants must have written documentation with patient-reported 100% compliance (ie, completed a 5 day course of nirmatrelvir/ritonavir). They must have symptom alleviation or resolution in COVID-19 signs/symptoms followed by a worsening (rebound) of signs/symptoms after completing an initial 5-day course of nirmatrelvir/ritonavir based on the judgement of both the participant and investigator ([Section 10.10.2](#)).
3. The onset of rebound in COVID-19 symptoms must occur within 2 weeks (14 days) after the completion of the initial 5-day course of nirmatrelvir/ritonavir.
4. Onset of rebound in signs/symptoms attributable to COVID-19 within 48 hours prior to randomization and ≥ 1 sign/symptom attributable to COVID-19 present on the day of randomization ([Section 10.10.2](#)).
5. SARS-CoV-2 infection as determined by rapid antigen testing in any specimen collected within 24 hours prior to randomization and collected within 2 weeks (14 days) after the completion of the initial 5-day treatment course of nirmatrelvir/ritonavir.
6. Has at least 1 characteristic or underlying medical condition associated with an increased risk of developing severe illness from COVID-19 ([Section 10.10.4](#)).

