10.3.1. Definition of AE

AE Definition

- An AE is any untoward medical occurrence in a patient or clinical study participant, temporally associated with the use of study intervention, whether or not considered related to the study intervention.
- Note: An AE can therefore be any unfavorable and unintended sign (including an abnormal laboratory finding), symptom, or disease (new or exacerbated) temporally associated with the use of study intervention.

Events Meeting the AE Definition

- Any abnormal laboratory test results (hematology, clinical chemistry, or urinalysis) or other safety assessments (eg, ECG, radiological scans, vital sign measurements), including those that worsen from baseline, considered clinically significant in the medical and scientific judgment of the investigator. Any abnormal laboratory test results that meet any of the conditions below must be recorded as an AE:
 - Is associated with accompanying symptoms.
 - Requires additional diagnostic testing or medical/surgical intervention.
 - Leads to a change in study dosing (outside of any protocol-specified dose adjustments) or discontinuation from the study, significant additional concomitant drug treatment, or other therapy.
- Exacerbation of a chronic or intermittent preexisting condition, including an increase in either frequency and/or intensity of the condition.
- New condition detected or diagnosed after study intervention administration, even though it may have been present before the start of the study.
- Signs, symptoms, or the clinical sequelae of a suspected drug-drug interaction.
- Signs, symptoms, or the clinical sequelae of a suspected overdose of either study intervention or a concomitant medication. Overdose per se will not be reported as an AE or SAE unless it is an intentional overdose taken with possible suicidal/self-harming intent. Such overdoses should be reported regardless of sequelae.

Events NOT Meeting the AE Definition

- Any clinically significant abnormal laboratory findings or other abnormal safety assessments that are associated with the underlying disease, unless judged by the investigator to be more severe than expected for the participant's condition.
- The disease/disorder being studied or expected progression, signs, or symptoms of the disease/disorder being studied, unless more severe than expected for the participant's condition.
- Medical or surgical procedure (eg, endoscopy, appendectomy): the condition that leads to the procedure is the AE.

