- Situations in which an untoward medical occurrence did not occur (social and/or convenience admission to a hospital).
- Anticipated day-to-day fluctuations of preexisting disease(s) or condition(s) present or detected at the start of the study that do not worsen.

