10.11. Appendix 11: Participant-Reported COVID-19-Related Signs and Symptoms

Sign and Symptom Collection[33]	Eligibility Criterion #5 Targeted (used for study entry)	Signs and Symptom Collection
Cough	X	X
Shortness of breath or difficulty breathing	X	X
Fever (documented temperature >38°C [100.4°F]) or subjective fever (eg, feeling feverish)	X	
Feeling feverish		X
Chills or shivering	X	X
Fatigue (low energy or tiredness)	X	X
Muscle or body aches	X	X
Diarrhea (loose or watery stools)	X	X
Nausea (feeling like you wanted to throw up)	X	X
Vomiting (throw up)	X	X
Headache	X	X
Sore throat	X	X
Stuffy or runny nose	X	X
Loss of smell	X	X
Loss of taste	X	X

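### The SAP defines treatment-emergent by event start alone, so an AE that begins before the first dose and worsens on treatment is not counted as a TEAE

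*SAP*

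**What the plan says.** SAP 3.5.1 sets the rule: "An AE is considered a treatment-emergent adverse event (TEAE) if the event started on or after the study medication start date and time". SAP 6.2.3 then summarizes TEAE incidence by treatment group, system organ class and preferred term in the safety analysis set, and adds no further condition. The protocol lists TEAE incidence as a secondary safety endpoint but does not define the term.

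Protocol 10.3.1 defines what an AE is, and the definition is not limited to new onset. It covers any unfavorable sign, "symptom, or disease (new or exacerbated) temporally associated with the use of study intervention". Among the events that qualify it lists "Exacerbation of a chronic or intermittent preexisting condition, including an increase in either frequency and/or intensity of the condition". Among those that do not, it lists "The disease/disorder being studied or expected progression, signs, or symptoms of the disease/disorder being studied, unless more severe than expected". It also excludes anticipated day-to-day fluctuation of conditions "present or detected at the start of the study that do not worsen".

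Protocol 8.4.1 starts active AE collection at informed consent, so an AE can be on record before the first dose. Protocol 4.1 places screening within 24 hours before randomization.

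**The concern.** The protocol accepts worsening as a way for an event to become an AE. The SAP does not accept it as a way for an event to become treatment-emergent. A program written to SAP 3.5.1 would look at the recorded start and drop anything dated before the first dose, however much worse it became afterwards.

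The point has some weight in this population. Inclusion criterion 4 (protocol 5.1) requires at least one "sign/symptom attributable to COVID-19 present on the day of randomization", so everyone enters with symptoms. The synopsis states: "The most common adverse events described with nirmatrelvir/ritonavir treatment are allergic reactions, change in taste, diarrhea, headache, and vomiting". Three of those five (diarrhea, headache and vomiting) also appear by name in the COVID-19 symptom list in protocol Appendix 11. The symptoms most likely to be made worse by the drug are thus ones that some participants may already have.

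Tolerability of a second course is part of the study's stated purpose. If worsening events were dropped, absolute TEAE incidence would be understated. If the same share were lost in each arm, the absolute difference would shrink by that share too.

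**Working it through.** No figure in the plan is at issue, so the check is a comparison of texts. The question for each kind of event is whether it is an AE under protocol 10.3.1 and, if so, whether it is a TEAE under SAP 3.5.1.

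1. *A COVID-19 symptom present on Day 1 that follows its expected course.* It is not an AE under protocol 10.3.1. It is absent from the TEAE table because of the protocol's AE definition, which is conventional, and not because of the SAP rule.

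2. *A COVID-19 symptom present on Day 1 that becomes more severe than expected after dosing.* It becomes an AE at that point. If its start is the date of worsening, it is a TEAE. If the site enters the date the symptom first appeared, it is not.

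3. *A chronic or intermittent condition that is exacerbated after dosing.* The exacerbation is an AE in its own right. The result again depends on which date is entered.

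4. *An AE recorded between consent and first dose that worsens after dosing.* If it stays one record with its pre-dose start, it is not a TEAE. If the worsening is entered as a separate AE, it is.

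The next question is whether anything in the documents settles the date. Protocol 10.3.3, under follow-up of AEs and SAEs, directs that new or updated information go into the documents originally submitted. A site could reasonably read that as updating the existing record and keeping its start. The same section has the investigator assign one intensity category to each AE. That does not prevent a worsening from being entered as a new AE, but nothing requires it. I found no rule in either document on whether a worsening gets a new record or which onset date applies.

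The last question is what is reported regardless of the TEAE rule. SAP 6.2.3 summarizes SAEs and AEs leading to discontinuation without limiting them to TEAEs. SAP 6.6 and 6.6.1 provide AE summaries and listings, also without that limit. What can be lost is therefore mainly nonserious events, and they are lost from the TEAE table rather than from the report.

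To size the loss one would need the number of AEs recorded before dosing, the share of these that worsen, and the share of exacerbations entered with their original onset. The documents give none of these. If every worsening is dated to itself, the loss is zero.

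**The case against.** The strongest reply is that the protocol already handles the case. A Day 1 COVID-19 headache of expected severity has no AE record and no AE start date. When it becomes more severe than expected, the event being dated is the worsening, which falls after dosing and meets SAP 3.5.1. To lose it, a site would have to date the AE to a time when the AE definition was not yet met. A genuine AE recorded before dosing has only a short window in which to arise. In addition, TEAE incidence is descriptive, with no hypothesis test, and the sponsor's reporting standards (SAP 3.5) or the CRF Completion Requirements document (protocol 10.1.7) may already contain the rule.

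Most of this stands, and it is why the point is small. It does not remove the point. Dating an exacerbation to its worsening is the natural reading, but neither document states it, and the follow-up wording in protocol 10.3.3 allows the other reading. For an AE on record before dosing, the SAP rule gives the wrong result as written unless a second record is made. The sponsor's standards and CRF guidance are not in the documents, so they cannot be relied on here.

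A reader might go further and infer that headache, diarrhea or vomiting present at baseline is generally lost from TEAE incidence, and might attach a percentage based on assumed symptom prevalence. The documents do not support that. Most such symptoms are not AEs until they exceed expectation, and any percentage would only restate the assumptions put into it.

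**Conclusion.** The point holds in a limited form. SAP 3.5.1 is narrower than the protocol's AE definition. An AE recorded between consent and first dose that worsens on treatment, or an exacerbation entered with its original onset, would not be counted as a TEAE. The gap is probably small, falls mainly on nonserious events and cannot be quantified from the documents.

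It would be tempting to read this as a bias between arms. Nothing in the documents points that way: assignment is randomized and double-blind, so there is no reason to expect sites to date events differently by arm.

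The conclusion assumes that the unseen reporting standards and CRF guidance do not already supply a worsening rule. If they do, the SAP is merely out of line with them. Severity: minor.

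**What to change.** Change SAP 3.5.1 to read: *An AE is a TEAE if it started on or after the first dose date and time, or started before it and increased in severity on or after it.*

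Add to the CRF guidance: *Record a worsening that meets the AE definition as a separate AE, with the date and time of worsening as its start.* The second line matters because one record with a single intensity grade may not show that severity rose after dosing.

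Leave the protocol's exclusion of expected COVID-19 symptoms as it is.

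The cost is one SAP clause and one line of guidance, with no new assessment. The downside is that a few of the added TEAEs may reflect the course of COVID-19 in both arms. If the sponsor's standards already contain the rule, the change only brings the SAP into line with them.
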